3.0 STUDY DESIGN

3.1 Study Description

This is a non-randomized, open-label Phase I trial in patients with Stage IV peritoneal surface dissemination from gastrointestinal, fallopian tube, ovarian, or primary peritoneal tumors enrolled at Duke Cancer Institute and select external collaborating institutions. All subjects will complete an extensive medical history, baseline physical examination and clinical assessment to ensure subject eligibility requirements (see Eligibility Criteria for details) within 4 weeks of starting study drug. All eligible patients must have a peritoneal catheter placed prior to the initiation of therapy. All patients will receive an initial seroconversion dose of talimogene laherparepvec 4×10^6 PFU on Cycle 1 Day 1 to enable seroconversion as described in the currently approved treatment protocol for the treatment of cutaneous melanoma. Three weeks (+3 days) after the initial seroconversion dose, patients will receive talimogene laherparepvec at the dose level for the cohort for which they are enrolled every 2 weeks (± 3 days) for up to 4 doses. The length of the first cycle is 5 weeks and subsequent cycles are 2 weeks in duration.

- Enrolled subjects are defined as subjects who give informed consent.
- Screen failures are defined as subjects who give informed consent and do not meet eligibility criteria.
- Accrued subjects are defined as subjects who give informed consent and meet eligibility criteria.
 - Withdrawal: Subject accrued but later withdrawn from the study, either before or after receiving a study drug.
 - Evaluable: In the Dose Escalation Cohort, subjects who are accrued, received study treatment, and completed the first cycle of safety assessments or have dose limiting toxicity (DLT) which is study treatment related that precludes completing the full cycle of assessments will be considered evaluable for DLT. All subjects (in Dose Escalation and Dose Expansion) who are accrued and receive any study treatment will be considered evaluable for toxicity. All subjects in Dose Escalation and Dose Expansion who are accrued and receive any study treatment will be considered evaluable for efficacy.
 - Non-evaluable: In the Dose Escalation Cohort, subjects who accrued but did not complete the first cycle of safety assessments due to reasons other than study treatment-

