related toxicity (e.g. disease progression or inter-current illness) are considered non-evaluable for DLT. All subjects (in Dose Escalation and Dose Expansion) who are accrued, received study treatment but did not complete initial restaging due to reasons other than disease progression (e.g. inter-current illness) will be considered non-evaluable for efficacy.

Table 3.1 Proposed Dose Levels

Dose Level	No. Evaluable Subjects	TVEC IP, once every 2 weeks x 4 doses*
Dose Escalation		
1 (starting dose)	3-6	4×10^6
2	3-6	4×10^7
3	3-6	4×10^8
Dose Expansion		
Expanded Cohort	6	MTD

*All patients will receive an initial seroconversion dose of 4×10^6 PFU. The first dose at each of these Dose Levels will be administered 3 weeks (+3 days) after the initial seroconversion dose, and then be given every 2 weeks \pm 3 days for a total of 4 doses at each Dose Level (in addition to the initial seroconversion dose, which all patients will receive).

Using a standard '3+3' dose escalation design, there are up to three dose levels that may be explored. See Table 3.1 for the dosing scheme.

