3.2 Dose Escalation

The first portion of the study will evaluate the toxicity profile of talimogene laherparepvec in patients with peritoneal surface dissemination from gastrointestinal, fallopian tube, ovarian, or primary peritoneal tumors.

Using a standard '3+3' dose escalation design, there are up to three dose levels that may be explored. Dose escalation will be dependent on dose-limiting toxicity (DLT) within the cohorts. The following are guidelines for dose escalation:

- Three (3) subjects will be accrued at the starting dose level. Subjects will be monitored for the first cycle (ie. first 5 weeks) before advancement to the next dose level. If no DLTs are seen, 3 subjects may be enrolled to the next dose level.
- If 1 of 3 subjects has a DLT at any dose level, then up to an additional 3 subjects will be enrolled at that dose level. If 1 of 6 subjects experience DLT at a given dose level, then escalation may continue to the next dose level.
- If 2 or more out of 3-6 subjects have DLT in any dose level, then that dose level will be considered to have unacceptable toxicity and the next lower dose level will have additional subjects enrolled to expand to 6 subjects. In this case, the next lower dose level will be declared as the MTD provided no more than 2 of 6 subjects have DLT.
- After the first dose level has completed enrollment, all enrolled subjects will complete at least the first 5 weeks of safety assessments. At that point, the PI, co-PI, and study chair will meet to review safety data for DLTs and determine whether enrollment can proceed at the next dose level. They will notify the funding company of the outcome of the meeting.
- In cases where the only toxicity seen at the lower dose level is Grade \leq 2, re-escalation for intermediate dosing will be considered.

- If there is uncertainty about study drug attribution to DLT, then re-escalation to the next dose level is permitted.
- If $\geq 33\%$ of subjects has DLT at any dose level, then that dose level will be considered to have unacceptable toxicity. The dose level immediately below the one with unacceptable toxicity will be MTD, provided that at least 6 patients have been enrolled to the lower dose level and it was deemed safe.
- If no unacceptable toxicity is seen at the highest dose level, then the highest dose level will be considered the MTD.
- Up to 6 subjects will be enrolled at MTD before proceeding to the Dose Expansion Cohort.

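### The six-subject conditions in the escalation and MTD rules (3.2) count enrolled rather than DLT-evaluable subjects, so they can be met with only three to five subjects observed

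*Combined protocol and SAP*

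**What the plan says.** Section 3.1 sets up three nested groups. "Enrolled subjects are defined as subjects who give informed consent". "Accrued subjects are defined as subjects who give informed consent and meet eligibility criteria"; the same list allows an accrued subject to withdraw before any study drug. In the Dose Escalation Cohort, a subject is evaluable for DLT if accrued, treated, and either "completed the first cycle of safety assessments or have dose limiting toxicity (DLT) which is study treatment related that precludes completing the full cycle". Those who do not finish cycle 1 for reasons other than treatment-"related toxicity (e.g. disease progression or inter-current illness) are considered non-evaluable for DLT". Table 3.1 then gives the size of each level under the column "No. Evaluable Subjects": 3-6 per escalation level and 6 in the expansion.

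The decision rules in 3.2 use other units:

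- First level: "Three (3) subjects will be accrued at the starting dose level".
- Next level: "If no DLTs are seen, 3 subjects may be enrolled to the next dose level".
- After one DLT in three, up to three more are enrolled, and one DLT in six subjects allows escalation.
- The percentage rule (33% or more) refers to plain subjects.
- The MTD is the level below the unacceptable one, "provided that at least 6 patients have been enrolled to the lower dose level and it was deemed safe".

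Section 10.5 sends the safety review to the rules in 3.2. Section 9.1.2 says the MTD is determined as described in Table 3.1. No section says that a subject not evaluable for DLT is replaced or removed from the denominator.

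**The concern.** A 3+3 rule treats each subject in the denominator as someone who was watched through the DLT window. A subject who leaves in cycle 1 for progression or illness was not, and 3.1 says as much. If that subject still fills one of the six places, the rule reads an unobserved subject as one without a DLT.

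The dosing schedule sharpens this. Every subject first receives the same seroconversion dose, and the cohort dose starts three weeks later, on Day 22. Someone who leaves before Day 22 never receives the cohort dose, yet would count towards six enrolled at that level. At levels 2 and 3 that subject has had no exposure at all to the dose being judged.

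At stake is the evidence behind the MTD, and so behind the dose used in the expansion cohort.

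**Working it through.** **The plan's own numbers.** Table 3.1 gives three levels of at most 6 evaluable: 3 × 6 = 18. Adding 6 in the expansion gives 18 + 6 = 24, which is the synopsis maximum of 24 evaluable. The synopsis also says that the escalation cohort will enroll 6 to 18, so 18 serves both as the enrolled and as the evaluable maximum, with no room for a replacement. Section 9.1 allows up to 30 enrolled and treated, which is 30 − 24 = 6 more than the evaluable maximum, but no rule links the two figures.

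**What each passage secures.** Table 3.1 asks for at least 3 evaluable at a level. The MTD condition in 3.2 asks for at least 6 enrolled. A level with 6 enrolled and 3, 4 or 5 evaluable satisfies both. The same holds for the one-in-six rule: three evaluable subjects with one DLT, then three more enrolled of whom not all are evaluable. The observed fraction behind one in six (16.7%) would then be 1/5 = 20%, 1/4 = 25% or 1/3 = 33.3%.

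**Effect on the six-subject check.** Let p be the true DLT rate and n the number actually observed. The documents state no p, so these rates are assumptions.

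P(at most 1 DLT) = (1 − p)^n + n·p·(1 − p)^(n−1)

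At p = 0.30:

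- n = 6: 0.7^6 + 6(0.3)(0.7^5) = 0.118 + 0.303 = 0.420
- n = 5: 0.7^5 + 5(0.3)(0.7^4) = 0.168 + 0.360 = 0.528
- n = 4: 0.7^4 + 4(0.3)(0.7^3) = 0.240 + 0.412 = 0.652

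| True DLT rate (assumed) | 6 observed | 5 observed | 4 observed |
|---|---|---|---|
| 0.20 | 0.655 | 0.737 | 0.819 |
| 0.30 | 0.420 | 0.528 | 0.652 |
| 0.40 | 0.233 | 0.337 | 0.475 |

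**Effect on the escalation step,** with the first three all evaluable as Table 3.1 requires, and m evaluable among the second three:

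P(cleared) = (1 − p)^3 + 3p(1 − p)^2 · (1 − p)^m

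At p = 0.30 this is 0.343 + 0.441 × 0.343 = 0.494 for m = 3, and 0.343 + 0.441 × 0.49 = 0.559 for m = 2. At p = 0.40 the values are 0.309 and 0.372.

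Both calculations take leaving cycle 1 early to be unrelated to DLT risk.

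**How often.** The documents give no non-evaluable rate. If it were 10% to 25% per subject, the chance of at least one non-evaluable subject among six would be 1 − 0.9^6 = 0.47 to 1 − 0.75^6 = 0.82. This range is illustrative only.

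**The case against.** The best reply is that the intended unit can be inferred. Table 3.1 sizes levels in evaluable subjects, 9.1.2 points to that table for the MTD, and the synopsis total is in evaluable subjects. The category of non-evaluable for DLT has no evident use except in these rules. Section 3.2 also has subjects monitored through cycle 1 before advancement, and 3.2 and 10.5 have the first level complete it before review. Taken strictly, enrolled would include screen failures, who cannot complete five weeks of on-treatment assessments, so 3.2 is not using the word as 3.1 defines it. The MTD condition also requires that the lower level be judged safe.

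Much of this stands. A reader might infer that a level can be cleared when only two of its first three subjects were observed. The documents do not support that: Table 3.1 sets a floor of three evaluable at every level, and the cycle 1 completion requirement adds to it at the first.

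A reader might also infer that, with one non-evaluable subject added, two DLTs could pass as 2/7 = 28.6%, below the 33% threshold. That fails too. The synopsis calls a level unacceptable once two or more subjects have a DLT, whatever the denominator. Section 3.2 caps a level at six, and a seventh subject would be there only because someone had been replaced, which already means counting evaluable subjects.

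What the reply does not reach is the six-subject conditions. A floor of three does not turn six enrolled into six evaluable, and the judgement of safety is made on whatever data those six supplied.

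**Conclusion.** The point holds as a mismatch of units between 3.2 and 3.1/Table 3.1, with consequences for the one-in-six rule and the MTD condition. It does not show a design that sets out to count unobserved subjects.

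At an assumed true DLT rate of 30%, the chance that a level shows at most one DLT rises from 0.42 with six observed to 0.53 with five and 0.65 with four. These figures apply only when subjects are in fact lost in cycle 1 and counted anyway. They describe the single check, not the operating characteristics of the whole escalation. The frequency of such losses cannot be taken from the documents. The background section's median survival of six months for peritoneal carcinomatosis makes early loss plausible, but it does not describe the eligible population.

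The matter is worth correcting because it concerns the threshold that names the MTD, and that threshold should not rest on inference.

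**What to change.** Reconcile 3.2, 10.5 and the synopsis with 3.1 and Table 3.1:

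- In each decision rule, name the DLT-evaluable subject as defined in 3.1 as the unit, for both numerator and denominator. The MTD condition would then require at least 6 DLT-evaluable subjects at the lower level.
- State that a subject not evaluable for DLT is replaced and is counted in neither numerator nor denominator.
- Label the synopsis figure of 6 to 18 in escalation as evaluable subjects, and say whether the limit of 30 in 9.1 is meant to cover replacements.

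The planned evaluable numbers do not change. The cost is a wording amendment and an occasional replacement subject, with the added time to observe that subject through cycle 1.

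A separate conflict needs attention in the same amendment. Section 3.2 accepts a lower level as MTD with up to 2 DLTs in 6, while 2/6 = 33.3% meets its own rule of 33% or more for unacceptable toxicity, as well as the rule of two or more DLTs in 3.2 and the synopsis. These passages disagree whichever subjects are counted, and the sponsor must reconcile them. Changing the unit will not do it.

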9.1.2 Primary Endpoint

The primary objective of the study is to define the safety and toxicity profile of talimogene laherparepvec in patients with peritoneal surface dissemination from gastrointestinal, fallopian tube, ovarian, or primary peritoneal tumors. The MTD across three dose levels will be determined as described in Table 3.1. The safety analyses will be performed on the safety population, as defined above. Incidence of adverse events occurring in 10% or more of patients will be summarized by Grade, overall and by dose level.

Adverse events will be described using the NCI CTCAE 5.0 criteria. Frequency and severity of adverse events according to the NCI CTCAE v 5.0 body system and severity criteria will be described. In addition, frequency of Grade 3 or 4 adverse events will be described separately. Causality will also be noted.

Laboratory assessments will also be described according to the NCI CTCAE criteria, with separate descriptions for Grade 3 or 4 laboratory abnormalities. Clinically significant laboratory abnormalities will be described as well. Serious adverse events will be summarized, including a causality assessment.

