10.4.2 Medication Overdose

If an adverse event(s) is associated with ("results from") the overdose of study drug(s), the adverse event(s) is reported as a SAE, even if no other seriousness criteria are met. Refer to SAE reporting procedures in [Section 10.2](#).

There is no clinical experience with overdosage of talimogene laherparepvec. Doses up to 4 mL at a concentration of 10^8 PFU/mL every 2 weeks have been administered in clinical trials with no evidence of dose limiting toxicity. The maximum dose of talimogene laherparepvec that can be safely administered has not been determined. In the event of a suspected overdose, the patient should be treated symptomatically and supportive measures instituted as required.

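### Section 3.2 names the top dose level the MTD whenever it is not rejected, so the trial can report an MTD with no upper bound, possibly on 0 DLTs in 3 subjects

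*Combined protocol and SAP*

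**What the plan says.** Section 3.2 gives two routes to an MTD.

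- **After a rejection.** A level is rejected under this rule: "If 2 or more out of 3-6 subjects have DLT in any dose level, then that dose level will be considered to have unacceptable toxicity". Then "The dose level immediately below the one with unacceptable toxicity will be MTD", on condition that at least six patients were enrolled at that lower level and it was judged safe.
- **At the top of the range.** "If no unacceptable toxicity is seen at the highest dose level, then the highest dose level will be considered the MTD". This sentence requires neither a rejected dose nor a minimum number of subjects. A later bullet has up to six subjects enrolled at the MTD before expansion, which is a ceiling and not a requirement.

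One DLT in six does not reject a level: "If 1 of 6 subjects experience DLT at a given dose level, then escalation may continue to the next dose level".

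The term is then used as if an MTD will always exist. Section 9.1.2 (Primary Endpoint) says "The MTD across three dose levels will be determined as described in Table 3.1". Section 9.1 defines the intent-to-treat population by treatment at the MTD. Section 9.1.4 treats defining the MTD as something the study does, and analyses efficacy in patients treated at it. Table 3.1 and Section 3.3 assign the expansion cohort to it. Section 10.5 gives the safety review two results: go to the next level, or MTD reached.

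On existing knowledge, Section 10.4.2 says "The maximum dose of talimogene laherparepvec that can be safely administered has not been determined", and that doses up to 4 mL at 10^8 PFU/mL "have been administered in clinical trials with no evidence of dose limiting toxicity".

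**The concern.** An MTD is informative because a higher dose was found intolerable. If level 3 passes, nothing was tested above it, and the supportable statement is that the MTD lies at or above the top of the tested range or was not reached. The rule instead produces the statement that the MTD is 4×10^8 PFU. A later reader, or the designer of a follow-on trial, could take this as evidence that higher doses are too toxic.

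The route that gives no upper bound also asks for the least evidence. A lower level must have six subjects before it can be called the MTD, while level 3 can take the label after three.

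**Working it through.** **Plan's own figures.** The stated maximum of 24 evaluable subjects reproduces as 3 levels × 6 + 6 in expansion = 24, which confirms the reading of the design. The documents give no target DLT rate, no expected DLT rate and no operating characteristics for the escalation rule, so there is no stated probability to reproduce.

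**Chance that level 3 is called the MTD with no dose rejected.** A level with true DLT rate p passes on 0/3, or on 1/3 followed by 0/3:

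P(pass) = (1−p)³ + 3p(1−p)² × (1−p)³

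| p | P(pass) |
|---|---|
| 5% | 0.973 |
| 10% | 0.906 |
| 15% | 0.814 |
| 20% | 0.709 |
| 25% | 0.600 |
| 30% | 0.494 |
| 40% | 0.309 |

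The chance that all three levels pass is the product. For 5/10/25%: 0.973 × 0.906 × 0.600 = 0.529. Enumerating every path, with a lower level expanded to six and accepted on at most 1/6, gives the full split. All rates are assumptions.

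| Assumed DLT rate, levels 1/2/3 | Level 3 called MTD, nothing rejected | MTD below a rejected dose | Level 1 rejected |
|---|---|---|---|
| 5/5/5% | 92.2% | 5.1% | 2.7% |
| 5/10/15% | 71.8% | 25.5% | 2.7% |
| 5/10/25% | 52.9% | 44.4% | 2.7% |
| 10/20/30% | 31.7% | 58.2% | 10.0% |
| 20/30/40% | 10.8% | 57.1% | 32.1% |

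With the same rate at every level, the second column crosses 50% at p = 16%.

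**Sensitivity.**
- If level 3 is always expanded to six before it is named, the second column becomes 91.7%, 68.5%, 47.1%, 27.0% and 8.2%.
- Section 3.2 also contains a looser condition for the lower level: "the next lower dose level will be declared as the MTD provided no more than 2 of 6 subjects have DLT". This conflicts with the two-or-more rule and with the 33% rule in the same section, and those passages must be reconciled. It acts only after a rejection, so it leaves the second column unchanged (52.9% at 5/10/25% either way).

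**What the label can rest on.** Exact one-sided 95% upper limits for the DLT rate at level 3:
- 0/3: 1 − 0.05^(1/3) = 63%
- 0/6: 1 − 0.05^(1/6) = 39%
- 1/6: the p that solves (1−p)^6 + 6p(1−p)^5 = 0.05, which is 58%

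**The case against.** The strongest reply is that this is a matter of naming. The protocol states its operational rule openly, Section 9.1.2 limits the MTD to the three levels, Section 3.2 also uses MTD/RPTD as one term, and Section 10.4.2 admits that the maximum safe dose is unknown. The primary objective in Section 2.1 is the toxicity profile, and adverse events are summarised by dose level. The same subjects are analysed and the same dose is expanded under either name. All of this is correct, and it limits the consequence to what the trial concludes. It does not remove the fault: Sections 9.1, 9.1.2 and 9.1.4 use MTD alone, and no section allows the result that it was not reached.

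A second reply is that wide upper limits belong to any 3+3 design, and that six more subjects are treated in expansion: 0/9 would give 28% and 0/12 would give 22%. The n = 12 in Section 9.1.3 also suggests that six at the MTD plus six in expansion were intended. The imprecision is indeed not peculiar to this rule. But the MTD is declared before expansion, Section 3.1 defines DLT evaluability only for the escalation cohort, and Section 3.2 requires six subjects only for a level below a rejected one.

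Two stronger readings are tempting and are not supported.

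- *That the trial will most likely end this way.* Section 10.4.2 is suggestive, since 4 mL × 10^8 PFU/mL = 4×10^8 PFU equals level 3 numerically. It gives no rate, denominator or route, however. Section 1.2.1 describes approved use by injection into tumours, while Section 6.2.2 specifies intraperitoneal infusion. At 10/20/30% the outcome is the less likely one.
- *That rejection of level 1 leads to the same false MTD.* It leads to no MTD. The condition on the lower level cannot be met, and Section 3.3 opens expansion only once an MTD exists. Section 11.7 leaves a discretionary route to amendment, de-escalation or closure, not tied to this event. What is missing is an explicit statement, which is a separate and minor point.

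**Conclusion.** The concern holds as a fault in what the trial may conclude. If no dose is rejected, Section 3.2 yields an MTD that is not bounded from above and may rest on three subjects, and Section 9 builds the intent-to-treat set and the primary endpoint on that label.

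Its frequency is conditional on assumed DLT rates. It is the more likely result if rates are about 16% or less at every level, or if they are low at levels 1 and 2 and rise to about 25% only at level 3 (53%, or 47% if level 3 is first expanded to six). It is the less likely result at higher rates (32% at 10/20/30%, 11% at 20/30/40%). The textual fault does not depend on these rates. It should be corrected, because the change is confined to wording and prevents an unsupported statement under the primary endpoint.

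**What to change.** 1. In Section 3.2, replace the top-dose sentence with: if level 3 is not rejected, it is reported as the highest dose tested and candidate RPTD, and the MTD is reported as not reached within the tested range.
2. Use one term for the dose carried forward, either expansion dose or MTD/RPTD defined in this way, in the synopsis, Table 3.1, Sections 3.2, 3.3, 9.1 to 9.1.4 and 10.5. Changing only some of these would create new inconsistencies.
3. Report the DLT rate at each level with an exact confidence interval.
4. As a minor separate item, Section 3.2 refers to a next lower level that Table 3.1 does not contain below level 1. The sponsor should reconcile the two and state how rejection of level 1 is reported. What then happens to the trial is the sponsor's decision.

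Cost: edits in several sections and a slightly less favourable headline if level 3 passes. There is no change to dosing, the escalation rule or the number of subjects.
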